4.13 Risks and Benefits

4.13.1 Potential Risks

Risks associated with sample collection

There is the potential for bleeding, bruising, discomfort, infections or pain at the needle site, or dizziness from the needle stick to take the blood samples.

There are no physical risks to the participant in releasing tumour samples for the purpose of this study since the tissue has already been obtained by a previous surgical/ biopsy procedure. In cases where tumour tissue is collected during a surgical procedure, the physical risks are those associated with the surgery being performed. Tumour tissue will only be collected after the specimen is removed from the patient's body and only if there is enough specimen available.

Risks associated with follow-up procedures

There are potential risks for study participants associated with the diagnostic evaluations following a “positive” cfDNA assay result. The diagnostic evaluations (procedure or imaging) will be deemed as appropriate by the Study Doctor and will reflect the current clinical standard-of-care surveillance guidelines for each respective HCS cohort. The potential risks associated with diagnostic evaluations will be explained to the participant during the consent processes, and again by their medical team prior to any diagnostic procedure or imaging. Potential risks associated with diagnostic evaluations include (but are not limited to):

- allergic reactions and respiratory problems, and in rare instances death from general anesthesia or sedatives that may be used with endoscopic procedures
- perforation of the colon, esophagus, or stomach by the colonoscope, sigmoidoscope, or endoscope
- prolonged or severe bleeding from endoscopy, colonoscopy, sigmoidoscopy, or laparoscopy injury
- infection from endoscopy, colonoscopy, sigmoidoscopy, or laparoscopy
- visceral injury and bleeding, injury to the bowel, or injury to the bladder from laparoscopy
- exposure to ionizing radiation from imaging procedures
- acute allergic or severe contrast reactions including acute renal failure, and in rare instances death from procedures using imaging contrast agents

If an abnormality is identified by a diagnostic procedure or imaging done in follow-up to a “positive” cfDNA assay result, additional investigations (e.g., imaging or biopsy) will be performed as part of the participants clinical care, and will be guided by the participant’s clinical team, or study investigator. Any biopsies and/or surgeries performed following identification of an abnormality by a diagnostic procedure or imaging, are no longer considered a study-related procedure or a risk detailed in this protocol.

Risks associated with the test result

There is a potential risk of receiving a “false positive” test result (i.e., a “positive” signal is detected on the cfDNA assay, but no cancer is present (i.e., no cancer is detected on any of the follow-up diagnostic investigations). This could result in unnecessary procedures and imaging, which can cause both physical and psychological risks to the participant.

There is also a potential risk of receiving a “false negative” test result (i.e., a “negative” signal is detected on the cfDNA assay, but cancer is present). This may result in non-compliance with a participant’s next standard-of-care cancer surveillance cycle, which

could cause a delay in a potential cancer diagnosis. During the consent process, and again at the time of cfDNA assay result disclosure, the study team will communicate to the participant that a “negative” cfDNA test result should not be interpreted as a definitive absence of cancer, and the cfDNA assay should not outweigh current clinical standard-of-care surveillance guidelines.

Risks associated with genetic testing

There is a risk that information gained from genetic research could be linked to the participant. To prevent this, all samples and data collected within this study will be identified by a unique study ID and all samples will also be tracked by a barcode. A list linking the study ID to participant information will only be made available to certain study team members, as permitted by REB. Samples will be held in a secure facility and will not be identified by the participant's name. The researchers believe the chance that someone will identify the participant is very small. Still, the risk may change in the future as people come up with new ways of tracing information and this will be communicated with the participant through the consent form.

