4.8 Collection of Clinical Data

Clinical data will be collected from participants' medical record and the medical history and demographic questionnaires completed by participants following informed consent (please see "Demographics and Medical History Questionnaire"). Participants will be given the option to complete the questionnaire in person (e.g., if the consent process occurred in person), or electronically. If completed electronically, the questionnaire may be emailed to the participant, or the participant may complete the questionnaire via REDCap (a link will be emailed to them). If a patient is not able to complete the questionnaire electronically, a physical copy may be mailed to them with a return envelope. The questionnaires will record the patient's study ID only (name, DOB, MRN will not be recorded). Updates to questionnaire results may be collected by the study team over the course of the study.

If a participant receives care at more than one study site, their medical records from any of the other sites may also be looked at, regardless of which site they are enrolled at for this study. Sharing of any study records between sites for patients who have received care at multiple sites will only occur following execution of appropriate DTAs. Study team members may also request medical history information from participants directly, if not available in their medical records (e.g. by setting up a phone call). Additionally, study team members may ask a participant to complete a Release of Information (ROI) form (appended to this application), to request medical records from external hospitals/clinics.

The following clinical data will be captured over the course of this study for all participants:

- Demographic information (including date of birth, self-reported gender and sex assigned at birth, ethnicity).
- Genetic diagnosis and date.
- Past medical history, including but not limited to personal history of cancer, cancer risk factors, cancer screening history, pregnancy status, current medications, comorbidities.
- Cancer screening – results and dates of any cancer screening/diagnosis investigations done prior to, or during the study (including the diagnostic investigations done in follow-up to a positive cfDNA test result).

- For participants with a history of cancer or diagnosed with cancer during the study – pathology information, imaging and procedure results, treatment details.
- Family history of cancer.

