6.0 Study Intervention

All study participants will continue to receive standard-of-care cancer screening over the course of this study, as they have prior to study enrollment. Study participants randomized into the experimental arm will provide blood samples 3 times a year for 4 years. cfDNA sequencing will be performed on blood samples collected from participants in the experimental group. Results of the cfDNA sequencing (either “cancer signal detected” or “cancer signal not detected”) will be communicated to the participant by a designated member of the study team. We expect up to approximately 5-10% of participants per year in the experimental arm will receive a “cancer signal detected” result, which will trigger follow-up diagnostic investigations to confirm if cancer is present or not (outlined in Appendix A: “Cohort Specific Diagnostic Workflows”). The type of follow-up diagnostic investigations will be consistent with standard-of-care recommendations.

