7.0 Assessment of Efficacy and Safety

There is a possibility that the sequencing tests (sWGS, targeted panel, cfMeDIP) are less sensitive than standard-of-care screening. We will continuously monitor the concordance between cfDNA assay results and standard-of-care surveillance results. Confirmation of a cancer diagnosis will be supported by imaging confirmation, pathologic confirmation, or another form of clinical confirmation deemed appropriate by the study investigator. Yearly, we will evaluate:

- the percentage of cancers found by standard-of-care screening missed by the cfDNA assay.
- the percentage of positive cfDNA results where no cancer is detected on any follow-up diagnostic investigations.

If we determine that one of the tests are consistently underperforming (e.g. if 50% of cancers found by standard of care screening are missed by cfDNA assay), we will consider discontinuing the underperforming assay, and replacing it with an alternative validated test (e.g. plasma WGS). If we change one or more of the assays over the course of the study, participants will be notified of this change verbally by a study team member. If no alternative test is available, we may decide to end the study early.

The Study Doctor will perform the following tasks to ensure the safety of subjects and the good conduct of the study, on a monthly basis:

- Review the study binder to ensure all documents and communications are up to date
- Review the Inclusion/Exclusion forms for completeness and compliance to study protocol
- Monitor the accrual rate and recruiting efforts
- Monitor the number of ‘false positive’ results, and the number of subsequent diagnostic investigations undergone by the participant
- Monitor participant compliance to routine cancer screening protocols

Study related adverse events will be documented and reported to the UHN REB, as per the standard institutional procedure.

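### Complications of biopsies and surgeries triggered by a positive cfDNA result have no stated recording route

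*Protocol*

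**What the plan says.** Section 4.13.1 (Potential Risks) describes what happens when the work-up of a positive cfDNA result finds an abnormality. Further investigation becomes clinical care and "will be guided by the participant’s clinical team, or study investigator". It then states: "Any biopsies and/or surgeries performed following identification of an abnormality by a diagnostic procedure or imaging, are no longer considered a study-related procedure". The same sentence adds that they are not a risk covered by the protocol either.

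Section 7.0 (Assessment of Efficacy and Safety) holds the only adverse event commitment in the protocol: "Study related adverse events will be documented and reported to the UHN REB, as per the standard institutional procedure". The protocol does not define the term study related.

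On false positives, section 4.13.1 says: "This could result in unnecessary procedures and imaging, which can cause both physical and psychological risks to the participant". It also lists harms of the first-line work-up as study risks, for example "infection from endoscopy, colonoscopy, sigmoidoscopy, or laparoscopy", together with perforation, bleeding, sedation, radiation and contrast reactions.

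Section 4.8 (Collection of Clinical Data) collects results and dates of screening and diagnostic investigations for all participants, including those done after a positive result. Pathology, procedure results and treatment details are listed under a narrower heading: "For participants with a history of cancer or diagnosed with cancer during the study".

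**The concern.** The trial adds a test to existing surveillance. Its benefit, earlier or additional cancer diagnoses, has to be weighed against invasive procedures in people who turn out not to have cancer. A biopsy or operation done because a positive cfDNA result led to an abnormal scan is part of what the testing strategy causes, whoever orders it and whatever budget it falls under.

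If the procedure is labelled not study-related and only study-related adverse events are documented, a bleed, infection or surgical injury from it may appear nowhere in the trial data. The result of the same biopsy does enter the data. Section 4.6 puts pathology first among the ways to confirm a cancer diagnosis, and section 8.0 names biopsy among the tests that confirm cfDNA findings for the predictive values. The procedure would then count towards test performance while its complications had no stated place on the harm side. An analysis plan cannot recover events that were never collected.

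**Working it through.** This is mainly a check of the text. The question is whether any stated data stream would capture a complication of a biopsy or surgery in a participant whose positive cfDNA result led to an abnormality that proved not to be cancer.

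1. **Adverse event reporting (7.0).** It covers study-related events. The term is undefined, and 4.13.1 is the only text that says whether these procedures are study-related. It says they are not. No route is stated.
2. **Monthly and yearly monitoring (7.0).** It counts false positives, the subsequent investigations, the percentage of positives with no cancer found, and cancers missed by the assay. It does not count complications.
3. **Clinical data for everyone (4.8).** It takes results and dates of investigations, so the biopsy itself should appear. Complications are not listed. An operation in someone without cancer may or may not be treated as an investigation.
4. **Procedure and treatment details (4.8).** These apply to participants with past or new cancer. That includes some currently cancer-free people, since section 5.2 admits those treated at least 3 years earlier. Complications are not listed here either.
5. **Morbidity and mortality comparisons (8.0).** They are confined to five named cancer sites and run from detection of a cancer, so they cannot capture harm in someone without cancer.

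None of the five names complications of these procedures.

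**Scale.** The inputs are:
- experimental arm of 500 (Protocol Summary);
- positive rate: "We expect up to approximately 5-10% of participants per year in the experimental arm" (6.0), worded as an upper limit;
- 4 years of testing (6.0);
- cancer detection of 5% up to 10% (8.0).

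Positives per year: 500 × 0.05 = 25, and 500 × 0.10 = 50.

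Distinct people with at least one positive over 4 years, with independent years and no dropout, are 500 × (1 − (1 − r)^4):
- r = 0.05: 500 × (1 − 0.8145) = 92.7, about 93.
- r = 0.10: 500 × (1 − 0.6561) = 171.95, about 172.

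Cancers in the arm: 500 × 0.05 = 25, and 500 × 0.10 = 50.

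The protocol gives no rate of biopsy or surgery after a positive result, so the calculation stops here.

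**The case against.** Four points on the other side have force.

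- **The exclusion is inferred.** The sentence in 4.13.1 is risk-disclosure text about procedures. Section 7.0 concerns events and defers to an institutional procedure that is not shown. An event in a clinical-care procedure could still be judged related to the study test. This stands as a limit on the claim: the protocol does not forbid recording. But it states no route, and its only text on the status of these procedures points away from one.
- **These are not the main harms.** A reader might infer that the principal downstream harms of false positives are left out. The documents do not support that. Perforation, severe bleeding, visceral injury, sedation and contrast harms of the first-line work-up stay listed. A false positive with a clean work-up never reaches the sentence in question. Investigations are counted, with results and dates.
- **The gap is not confined to one arm.** A reader might infer undercounting in the experimental arm only, and hence a demonstrated bias towards cfDNA testing. Controls also have surveillance findings biopsied in usual care, and no field captures their complications either. Section 8.0 describes no between-arm safety comparison. What can be said is that the additional, cfDNA-triggered procedures arise in the experimental arm, so the missing information bears on what the test adds.
- **No minimum count of false positives follows.** Subtracting 25-50 cancers from 93-172 positives gives 43 (93 − 50) to 147 (172 − 25). A reader might take this as a floor. It is not, because the positive rate is an upper limit. Going on to a number of procedures would need a biopsy rate that the documents do not contain.

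It can also be said that fields and tables belong in a data or analysis plan. That holds for table layout. The scope of adverse event documentation and the list of clinical data are set in this protocol.

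**Conclusion.** The point holds in a limited form. Sections 4.13.1 and 7.0 together leave complications of biopsies and surgeries triggered by a positive cfDNA result without a stated recording route, and section 4.8 does not supply one. This sits badly with the protocol's own statement that false positives can lead to unnecessary procedures, with the study investigator's possible role in guiding them, and with the use of pathology to confirm cancer.

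The gap concerns complications, and possibly surgeries in people without cancer. It exists in both arms. Its consequence is an incomplete harm side of the comparison, not a demonstrated bias.

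The size is only indicative: about 93-172 people with a positive result over 4 years against 25-50 cancers. This assumes that the upper-limit rates apply every year, that years are independent and that nobody drops out. It shows that positives without cancer could be numerous at those rates. It does not show how many would have a biopsy or operation, or how many complications would follow.

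The conclusion also assumes that neither the institutional procedure nor the appended diagnostic workflows, which are not shown, already provides for these events. If either does, the protocol should say so.

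**What to change.** Reconcile sections 4.13.1, 7.0 and 4.8:

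- **4.13.1 and 7.0:** these biopsies and surgeries can remain clinical care, but state that their complications are documented as possible harms of the cfDNA testing strategy.
- **4.8:** add complications of biopsies and surgeries for suspected cancer to the items collected for all participants in both arms, and make clear that surgeries in people without cancer are included.
- **Reporting:** present these complications by arm and by whether cancer was confirmed.

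This changes what is recorded, not how anyone is managed. The cost is an amendment, a few extra chart fields within a record review that already runs for up to 7 years, and one table. The downside is more events to record and a possibly less favourable safety summary.

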4.13.2 Potential Benefits

Some participants will receive a “positive” cfDNA assay result, and the follow-up investigations may lead to a diagnosis of cancer, which can then be treated appropriately. The cancer diagnosis may happen earlier than if the participant were not involved in the study, and only partaking in standard-of-care surveillance.

This study will help evaluate the feasibility and acceptability of implementing cfDNA sequencing as part of standard-of-care surveillance for high risk patients. Should this study show benefits for detection of cancer in HCS patients comparable to current surveillance protocols, this may have broader implications for HCS families across Canada.

5.0 Selection of Subjects

This study will enroll 1000 participants across Canada. Up to 1000 will be enrolled at UHN. Participants will be recruited from the genetics, surgical, medical, and radiation oncology clinics. If other sites join our study, the appropriate MTAs and DTAs will be established, and samples collected at other institutions (who have institutional REB approval for the study) will be sent to UHN for analysis. We are still in the process of determining which other sites will be involved in our study. Other sites may include: BC Cancer Agency, Mount Sinai Hospital, SickKids Hospital, Women’s College Hospital, Sunnybrook Hospital, McGill Research Institute, Jewish General Hospital, IWK Health Centre, Eastern Health. If the patient receives care at more than one of the above sites, their medical records from any of the other sites can also be looked at, regardless of which site they are enrolled at for this study.

5.1 Subject inclusion criteria.

Patients must fulfill the following criteria:

1. Patients with a confirmed diagnosis of HBOC, LS, NF1, LFS, PALB2, and HDGC (i.e., patients with an identified pathogenic variant in the respective cancer predisposition gene, or patients with uninformative genetic testing but with a family history suggestive of the cancer predisposition syndrome).
2. Patients must be receiving standard-of-care clinical assessment for cancer by a managing physician under a provincial screening program or cancer surveillance protocol.
3. All patients must have signed and dated an informed consent form for this study.

5.2 Subject exclusion criteria.

1. Patients must not have a personal history of cancer diagnosed and treated within 3 years prior to the expected first sample collection date for this study. If a patient has a personal history of cancer, treatment must have been completed successfully at least 3 years prior to first study sample collection.
2. Patients diagnosed more than 3 years prior to the expected first sample collection date, but never been treated for the cancer.
3. Patients undergoing investigations for a clinical suspicion of cancer.
4. Patients who are not able to comply with the protocol (i.e., tri-annual blood sample collection if randomized into the experimental cohort).

5.3 Withdrawal of Subjects

If at any time a participant is found to be ineligible, as outlined in the inclusion and exclusion criteria, the participant will be removed from the study. In addition, if after obtaining informed consent the participant decides that they do not want to participate in the study, they may withdraw at any time at their own request. A participant may also be withdrawn from the study by the study team if not compliant with study requirements (e.g., completion of tri-annual blood collections if randomized into the experimental cohort).

If a participant is withdrawn from the study, the study team may continue to use the samples and corresponding data collected prior to withdrawal, unless the participant requests destruction of any samples not tested. Participant preferences will be documented by the study team. The study team will inform the participant that it is not possible to destroy samples and data which have already been processed and analyzed for research.

No study activities (including blood collections, questionnaires, data collection) will be completed for withdrawn participants. Any cfDNA test results received by the study team after a participant is withdrawn, will not be disclosed to the participant. Any diagnostic investigations following a positive cfDNA test result will not be initiated by the study investigator for withdrawn participants.

Withdrawn participants may be replaced by the study team, via the recruitment methods outlined above.

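### The removal rule in section 5.3 does not tie eligibility to status at randomisation, so it conflicts with the retention described elsewhere and leaves room for outcome-prompted removal

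*Protocol*

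**What the plan says.** Section 5.3 makes removal mandatory and sets no time limit: "If at any time a participant is found to be ineligible, as outlined in the inclusion and exclusion criteria, the participant will be removed". The consequences follow in the same section: "No study activities (including blood collections, questionnaires, data collection) will be completed for withdrawn participants", and "Withdrawn participants may be replaced by the study team". Data gathered before withdrawal may still be used. By contrast, withdrawal for not meeting study requirements, such as the blood draws, is left to the team's discretion.

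The criteria that the rule points to are in sections 5.1 and 5.2. Exclusion 1 is dated: it concerns cancer diagnosed and treated "within 3 years prior to the expected first sample collection date for this study". Exclusion 2 is tied to the same date. Exclusion 3 carries no date: "Patients undergoing investigations for a clinical suspicion of cancer". Nor does inclusion 2: "Patients must be receiving standard-of-care clinical assessment for cancer by a managing physician under a provincial screening program or cancer surveillance protocol".

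Elsewhere the protocol keeps participants in the study:
- Section 4.7 provides for optional further blood samples when someone in either arm is diagnosed on study.
- Section 4.8 (Collection of Clinical Data) gathers investigations, pathology and treatment arising during the study, for all participants, for up to 7 years.
- Section 7.0 plans a yearly count of cancers that routine screening found and the assay missed.

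Section 4.10 states that the study is not blinded.

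**The concern.** The undated criteria describe states that lie on the path to the endpoint. A participant whose routine scan or symptoms raise suspicion is under investigation shortly before diagnosis. Someone who drops out of surveillance no longer meets inclusion 2, and section 4.13.1 itself lists such a lapse among the risks of a false-negative result: "This may result in non-compliance with" the next round of surveillance. Under section 7.0 the Study Doctor reviews eligibility forms and screening compliance every month, so these states would come to notice.

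A rule that can be triggered by the approach of the outcome, or by a consequence of the test result, and that then stops data collection, can distort a comparison of detection rates and times to diagnosis. A statistical analysis plan could define the analysis set, but it could not recover outcomes that were never collected.

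**Working it through.** **1. The passages side by side**

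| Point | Section 5.3 with 5.1 and 5.2 | Other sections |
|---|---|---|
| Work-up on study | Exclusion 3 is undated; removal is mandatory once ineligibility is found | 4.1, 4.6 and 6.0: work-up after a positive result is a planned procedure |
| Diagnosis on study | Usually preceded by a state that meets exclusion 3 | 4.7: participant stays, either arm |
| Clinical data | None after withdrawal | 4.8: all participants, up to 7 years |
| Cancers missed by the assay | Experimental participants in a routine work-up could be removed | 7.0: counted yearly, so they must be kept |
| Lapse from screening | Inclusion 2 is undated | 7.0: monitored, with no removal stated |

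Section 5.3 also sits uneasily with itself. Exclusion 4 (inability to comply with the protocol) is undated too. Under the mandatory sentence it could turn the discretionary withdrawal for non-compliance into a compulsory one.

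**2. The two readings**

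- *Literal: the criteria apply continuously.* Removal could occur in either arm during a work-up or after a lapse. This cannot be squared with 4.7, 4.8 or 7.0.
- *Natural: an entry error comes to light later.* The conflict largely disappears, but a gap remains. A suspicion, diagnosis or positive cfDNA result soon after enrolment invites a chart review, which may show that a work-up was already under way at entry. The re-check is then prompted by the outcome or the result, made by people who know the arm, and followed by removal without further data and possibly by replacement. Participants without such an event are less likely to be re-checked.

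**3. Illustration of scale**

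The protocol gives no figure for removals, so the shares below are assumptions. Inputs from sections 4.1 and 8.0: n = 500 per arm; detection 5% in controls and up to 10% with cfDNA; two-sided alpha 0.05.

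If a share f of an arm's cancers is lost, the observed rate is p(1 − f), with the denominator held at 500. Power uses the pooled-variance formula, with p̄ the mean of the two rates:

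Φ{ [ |p2 − p1| − 1.96·√(2p̄(1 − p̄)/n) ] / √( [p1(1 − p1) + p2(1 − p2)]/n ) }

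Without losses there are 500 × 0.05 = 25 and 500 × 0.10 = 50 cancers, a difference of 5 points and power of 85%.

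| Share lost | Both arms: difference (power) | Controls only: difference | Experimental only: difference |
|---|---|---|---|
| 10% | 4.5 points (81%) | 10 − 4.5 = 5.5 | 9 − 5 = 4.0 |
| 25% | 3.75 points (73%) | 10 − 3.75 = 6.25 | 7.5 − 5 = 2.5 |
| 50% | 2.5 points (55%) | 10 − 2.5 = 7.5 | 5 − 5 = 0 |

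With no true difference (5% in both arms), losing 25% or 50% of control cancers only would give about a 16% or 55% chance of a significant result favouring cfDNA.

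The table shows that the sign of the bias depends entirely on which arm loses cancers, and the protocol does not settle that.

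The power statement in section 8.0 (above 97% for a 2-point increase) plays no part here. The same formula gives 26.5% for 5% against 7% at 500 per arm, so that statement is not reproduced, but this is a separate matter.

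**The case against.** The strongest reply is that the literal reading is not what the protocol describes. The criteria stand under selection of subjects and are checked before enrolment with a screening checklist (section 11.1). Finding someone ineligible ordinarily means discovering that they should not have been entered, and the reference to any time may say only when the error surfaces. Applied literally, the rule would remove nearly every control before diagnosis and leave section 8.0 nothing to compare. This objection stands.

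A reader might therefore infer too much in three ways:

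- *That participants are removed just as the outcome occurs.* No section says that an on-study work-up triggers removal, and 4.7, 4.8 and 7.0 point the other way.
- *That a lapse from screening leads to removal.* This is inference. Section 7.0 only monitors compliance, and the compliance ground in 5.3 concerns study requirements and is discretionary.
- *That the bias favours cfDNA.* It might, because clinical suspicion is the usual control route to diagnosis, while a work-up after a positive result is a study procedure. But experimental participants also keep routine surveillance, and if a positive result were taken as clinical suspicion the losses would fall mainly on their arm.

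Nor does 5.3 say that withdrawn participants are dropped from the analysis; their earlier data may be used. What is lost is everything afterwards.

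The objection does not close the gap under the natural reading. Nothing in 5.3 limits the re-check to pre-randomisation facts or keeps the person deciding unaware of arm and result.

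**Conclusion.** The point holds as a defect of drafting with a possible statistical consequence. Section 5.3 does not tie ineligibility to entry, two of the criteria it invokes are undated changing states, and the result conflicts with sections 4.7, 4.8 and 7.0 if taken literally. Even if taken as the discovery of entry errors, it permits unblinded removal of randomised participants, prompted by the outcome and without follow-up.

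Neither the size nor the direction of any bias can be derived from the documents. The shares of 10%, 25% and 50% are assumptions that show only sensitivity: with about 25 control cancers expected, each cancer lost moves the observed control rate by 1/500 = 0.2 points. The documents do not show that the trial removes participants in this way. They show that the text does not prevent it.

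**What to change.** Amend section 5.3 as follows:

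- State that eligibility is judged on status at randomisation only, leaving the dates within exclusions 1 and 2 as they are. A cancer work-up, a diagnosis or a lapse from surveillance that arises afterwards is not ineligibility.
- Allow exclusion after randomisation only where information dated before randomisation shows that a criterion was unmet, judged by someone who knows neither the arm nor any cfDNA result.
- Report such exclusions by arm.
- Reconcile 5.3 with 4.7 and 4.8, so that the rule on ending data collection and the commitment to follow all participants for up to 7 years agree.

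The cost is a one-paragraph amendment, with no added participants or procedures. The downside is that a few people who lapse from screening, or who were wrongly enrolled, stay in the analysis. The change is best made before the rule is applied, since outcomes not collected may be unrecoverable.
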